3. DESCRIPTION OF DESIGN AND TRIAL POPULATION

3.1 OVERALL TRIAL DESIGN AND PLAN

This phase III open-label, multi-centre randomised trial is designed to evaluate the efficacy and safety of Afatinib versus methotrexate as the second-line treatment of patients with R/M HNSCC who have progressed after prior platinum based chemotherapy for R/M disease in Asia/MENA region. Prior treatment with immunotherapy will be allowed. The primary endpoint of the trial is progression free survival (PFS).

Eligible patients will be stratified into four strata based on two stratification factors: ECOG performance score (0 vs. 1) and prior use of EGFR-targeted antibody therapy in the recurrent/metastatic setting.

[figure not shown]

Figure 3.1: 1 Trial design

Patients randomised to Afatinib treatment will receive continuous daily treatment with Afatinib until tumour progression, unacceptable adverse events or other reasons necessitating treatment permanent discontinuation (refer to [Section 3.3.4](#)). The starting dose of Afatinib will be 40 mg once daily. In the event of no or minimal AEs after the first four weeks of treatment or later, the dose will be increased to 50 mg (see [Section 4.1.4.1](#) for details). The dose will be reduced in the

Proprietary confidential information. © 2019 Boehringer Ingelheim International GmbH or one or more of its affiliated companies

event of certain drug-related AEs. The dose reduction will be in decrement of 10 mg, with the lowest dose being 20 mg. Patients receiving 20 mg will be permanent discontinued from treatment if a drug reduction AE still occurs ([Section 4.1.4.1](#)).

Patients randomised to methotrexate treatment will receive methotrexate weekly until progression, unacceptable AEs or other reasons necessitating treatment permanent discontinuation (refer to [Section 3.3.4](#)). The treatment will be administered as intravenous bolus injections at the starting dose of 40 mg/m² once a week with the option to increase the dose to 50 mg/m² in the event of no or minimal drug-related AEs after at least two-week treatment (see [Section 4.1.4.2](#) for details). The dose of methotrexate should be reduced in decrements of 10 mg/m² in case of drug-related AEs, see Section 4.1.4.2, but should not be below 20 mg/m².

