All patients will visit the investigational site weekly for assessment of safety parameters and AEs. Tumour response will be assessed regularly by CT scan/MRI (see [Flow Chart](#)) until progression. At disease progression, confirmed by tumour imaging, patients will be discontinued from the study medication.

The end of treatment (EOT) is defined as permanent discontinuation of Afatinib or methotrexate. Related EOT information needs to be obtained. Patients who permanently discontinue the study medication for any other reason than progression of disease (or withdrawal of consent) should continue the scheduled tumour imaging visits until progression as described in [Section 6.2.3](#). The requirement to continue imaging for study purposes for such patients will be removed following the database lock for primary analysis.

Following the EOT visit, patients should come to a follow-up visit (FUV) and then continue in the observational period. During the observational period, data of survival (vital status), related SAEs/AESIs and concomitant anti-cancer therapy will be collected. For patients who progressed on treatment, the observation period for overall survival starts after the FUV (end of residual effect) visit. For patients who have not progressed on treatment, this period starts after the last additional FU visit. A patient is considered to have completed the trial following death, withdrawal of consent or lost to follow-up.

Primary statistical analyses will be performed when the required number of progression free survival events has occurred as described in [Section 7.6](#). The clinical trial report will be written based on primary analysis results. An addendum to the clinical trial report may be used to summarise data collected beyond database lock for the primary analysis.

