3.2 DISCUSSION OF TRIAL DESIGN, INCLUDING THE CHOICE OF CONTROL GROUP

The trial is designed with two parallel arms in order to assess efficacy and safety of Afatinib versus methotrexate, administered as monotherapy in combination with BSC. Patients will be randomised to either treatment arm in a 2:1 ratio since this will enhance controlled collection of safety data for Afatinib for the investigated patient population. Following progression after standard platinum-based therapy for R/M HNSCC, there is no world-wide standard treatment. Erbitux® has been approved for this indication in the US based on response rate in a single arm trial without comparison to an active control. Methotrexate is mentioned as one of active single chemotherapeutic agents in the National Comprehensive Cancer Network (NCCN) guidelines. Weekly methotrexate administration is an acceptable treatment choice for R/M HNSCC patients who have failed to platinum-based therapy ([R10-5909](#)). Methotrexate is therefore selected as comparator for this trial.

The trial is open-label, partly due to the substantial differences in the safety profiles of the two investigational products, which could potentially reveal the blinding. The main reason for choosing an open-label design is the different administration routes of Afatinib and methotrexate, where blinding would mean that two thirds of the patients would receive placebo intravenous bolus injections weekly, which might not be ethical. Efforts are made to minimize bias, e.g., the primary analysis will be based on assessments of an independent, central imaging review committee who will evaluate tumour scans/images for each patient in a blinded manner.

The first disease evaluation will be done after 6 weeks of treatment in order to allow sufficient time to observe benefit from either drug. Six week duration is considered adequate to assess response although maximal tumour shrinkage may be seen later. To better assess any potential differences in the primary endpoint, PFS, tumour imaging assessments are required every 6 weeks for the first 24 weeks on treatment. Subsequent tumour evaluation will be done every 8 weeks. After the database lock for primary analysis, the imaging intervals can be changed to follow local site standard (if no standard; every 16 weeks).

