The dose of Afatinib must be escalated to 50 mg (at the earliest after 28 days on study medication) if all the following criteria are met:

- CTCAE grade ≤ 1 skin rash (any aetiology/relation)
- Absence of diarrhoea, mucositis, and/or any drug-related event (any grade) other than skin rash CTCAE grade 1 and
- Compliance of Afatinib intake is in 80~100% as described in [Section 4.3](#)
- Dose was not previously reduced due to any of the AEs depicted in the dose reduction scheme (see [Table 4.1.4.1: 1](#))

Dose escalation is prohibited in any situation other than that described above. The patient should remain on 50 mg unless dose reduction becomes necessary (see Table 4.1.4.1: 1).

Dose reduction, Afatinib

Treatment related AEs will be managed by treatment interruptions and subsequent dose reductions of Afatinib according to the schedule described in Table 4.1.4.1: 1. Dose reductions

Proprietary confidential information. © 2019 Boehringer Ingelheim International GmbH or one or more of its affiliated companies

will apply to individual patients only. Once the dose has been reduced, it may not be increased later.

Table 4.1.4.1: 1 Afatinib dose reduction scheme

| AE type and CTCAE grade |
|--|
| Events related to study medication; 
• Any drug related AE grade ≥ 3.• Diarrhoea grade ≥ 2 persisting for 2 or more consecutive days (≥ 48 hours) despite adequate anti-diarrhoeal medication/hydration.• Nausea and/or vomiting grade ≥ 2 persisting for 3 or more consecutive days despite anti-emetic treatment/hydration.• Reduced renal function to grade ≥ 1 as measured by serum creatinine, proteinuria, or glomerular filtration rate. |
| Action |
| Interrupt Afatinib treatment until patient has recovered to grade ≤ 1 (note for reduced renal function, recovered to grade <1) or to the CTCAE grade present at baseline ¹ . If patient has not recovered within 14 days, study medication should be permanently discontinued ² . |
| Dose reduction scheme |
| Resume treatment at reduced dose according to; 
• 40 mg if the dose prior to the interruption was 50 mg.• 30 mg if the dose prior to the interruption was 40 mg.• 20 mg if the dose prior to the interruption was 30 mg. No dose reduction is allowed below 20 mg. |

1 Baseline is defined as the CTCAE grade prior to start of treatment

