5.1 PRIMARY ENDPOINT

The primary endpoint in this study is progression-free survival (PFS), defined as the time from the date of randomisation to the date of disease progression evaluated according to RECIST 1.1 or to the date of death from any cause, whichever occurs first.

The disease progression status and date of progression will be assessed at the investigational sites, as well as by an independent central review board, comprising of three radiologists (two primary readers and one adjudicator as needed). As stated in the CTP and [Section 7.4](#) below, the primary analysis of PFS will be based on independent central review.

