6. GENERAL ANALYSIS DEFINITIONS

6.1 TREATMENT

In the clinical trial report, all randomized patients will be classified into either ‘Afatinib 40’ or ‘MTX 40’. For efficacy analyses, patients will be analysed as randomised. For safety analyses, patients will be analysed as treated, according to the initial treatment taken.

Even though this trial is open-label, according to BI SOP [1], report planning will be done in a ‘blinded’ manner. Therefore, before database lock, all patients will be randomly assigned a dummy treatment code, DummyRed or DummyBlue, and displayed as such in all programmed tables, listings and figures (TLFs).

For safety reporting purpose, the following treatment periods are defined:

- Screening: from informed consent to the date of first dose of study medication
- On-treatment: date of first dose of study medication to last dose
- Post-treatment: date of last dose + 1 day to the 28th day after last dose
- Post-study: from 29th day after last dose onwards

In summarizing the safety data, all adverse events with onset date during the on- and post-treatment periods will be considered as ‘treatment-emergent’. Refer to [Section 7.8.1](#) for more details.

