7.8.1 Adverse events

Unless otherwise specified, the analyses of adverse events (AEs) will be descriptive in nature. All analyses of AEs will be based on the number of patients with AEs and NOT on the number of AEs.

Furthermore, for analysis of AE attributes such as duration, severity, etc, multiple AE occurrences collected on the CRF will be collapsed into AE episodes provided that all of the following applies:

- The same MedDRA lowest level term was reported for the occurrences
- The occurrences were time-overlapping or time-adjacent (time-adjacent if the second occurrence started on the same day or on the day after the end of the first occurrence)
- Treatment did not change between the onset of the occurrences OR treatment changed between the onset of the occurrences, but no deterioration was observed for the later occurrence

For further details on summarization of AE data, please refer to the guideline 'Handling and summarization of adverse event data for clinical trial reports and integrated summaries' [9].

The analysis of adverse events will be based on treatment-emergent adverse events, i.e. all adverse events with an onset date between first drug intake and 28 days after last drug intake. All adverse events occurring before first drug intake will be assigned to 'screening' and all adverse events occurring after last drug intake + 28 days will be assigned to 'post-study'. For details on the treatment definition, see [Section 6.1](#).

An overall summary of adverse events will be presented. This summary will exclude the rows 'Severe AEs', and 'Other significant AEs' but will include additional rows for 'AEs leading to dose reduction', 'AEs leading to permanent discontinuation of study drug', and 'AEs by highest CTCAE grade'.

The frequency of patients with adverse events will be summarised by treatment, primary system organ class (SOC) and preferred term (PT) of MedDRA (using the version that is current at the time of analysis). All tables will be sorted by SOC according to the standard sort order specified by the European Agency for the Evaluation of Medicinal Products (EMEA); PTs will be sorted by frequency (within SOC). Frequency tables will be created for the following events:

- All AEs
- Drug-related AEs
- AEs leading to dose reduction
- AEs leading to treatment discontinuation
- Drug-related AEs leading to treatment discontinuation
- Serious AEs
- Drug-related serious AEs
- Fatal AEs

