These tables will be further categorised by highest CTCAE grade, including all grades, Grade 1-5.

In addition, preferred terms have been grouped to capture similar events, e.g. skin reactions that include rash, acne etc. Six grouped terms (rash/acne, stomatitis, ocular effects, lip effects, nail effects and fatigue) have been formulated for afatinib. These grouped terms are carefully reviewed by the Team Member Drug Safety for afatinib for each MedDRA version and maintained at the substance data base. The above frequency tables will be repeated using these grouped terms and remaining MedDRA PTs (i.e. the original PTs under these grouped terms will not be displayed). The tables will be sorted by descending frequency.

Additional AE tables will be produced for AEs of special interest (diarrhoea, the grouped term of rash/acne, stomatitis, renal insufficiency, hepatic impairment, and hematological events), providing further details on highest CTCAE grade, action taken with study drug and time to first onset of AE etc.

In recent trials, it has been observed that patients treated with an EGFR TKI who develop rash events tend to have better response and progression free survival. In order to explore this effect in this study, afatinib-treated patients will be grouped by the occurrence of CTCAE grade ≥ 2 rash/acne events and provide descriptive statistics for objective response and progression free survival. This analysis is exploratory in nature and not for comparison with methotrexate, therefore will be limited to afatinib patients only.

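### The rash-versus-outcome comparison counts rash over a window that lengthens with PFS, so it can favour the rash group when there is no association

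*SAP*

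**What the plan says.** SAP 7.8.1 notes that patients on EGFR tyrosine kinase inhibitors who develop rash have tended to respond better and to have longer PFS. To explore this, "afatinib-treated patients will be grouped by the occurrence of CTCAE grade ≥ 2 rash/acne events and provide descriptive statistics for objective response" and for PFS. The SAP calls this exploratory, limits it to afatinib patients and rules out comparison with methotrexate.

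The grouping is by any occurrence. The counting window is set in the same section, which analyses "all adverse events with an onset date between first drug intake and 28 days after last drug intake". SAP 6.1 agrees: "all adverse events with onset date during the on- and post-treatment periods will be considered as" treatment-emergent, with the post-treatment period ending 28 days after last dose.

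Three further statements matter:
- PFS is "defined as the time from the date of randomisation to the date of disease progression evaluated according to RECIST 1.1", or to death if earlier (SAP 5.1).
- "Patients randomised to Afatinib treatment will receive continuous daily treatment with Afatinib until tumour progression", unless adverse events or other reasons stop it sooner (Protocol 3.1). The same section adds: "At disease progression, confirmed by tumour imaging, patients will be discontinued from the study medication".
- "The first disease evaluation will be done after 6 weeks of treatment" (Protocol 3.2).

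Neither document gives an onset time for rash. Protocol 1.2.3 and 4.2.3.1 give one only for diarrhoea.

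**The concern.** The last dose follows progression, and the rash window follows the last dose. A patient who progresses early has few weeks in which to be recorded with rash, and a patient who progresses late has many. Rash-prone patients with short PFS are therefore more likely to end up in the no-rash group. This is guarantee-time (immortal-time) bias, and it points towards the hypothesis under study.

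The protocol makes some late rash plausible. Protocol 1.2.3 describes rash as dose-dependent, and Protocol 4.1.4.1 requires escalation, no earlier than 28 days, in patients who have had at most grade 1 rash and meet the other criteria. Patients without early grade 2 rash who stay on drug can therefore have a later period of risk.

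At stake is how one table is read. Median PFS by rash status invites the conclusion that rash marks benefit, and the planned comparison cannot separate that from the artefact.

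**Working it through.** **Inputs from the documents.** 220 afatinib patients (Protocol synopsis); exponential PFS with median 3.0 months, about 91.3 days (Protocol 7.6); scans at weeks 6, 12, 18 and 24, then every 8 weeks (Protocol 5.1.2.1); rash counted to last dose + 28 days (SAP 7.8.1); response rate 10.2% from the earlier global trial (Protocol 1.2.3).

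**Assumptions.** 40% of patients rash-prone (20% and 60% also tried); exponential rash onset, independent of PFS, with median 1, 2, 4 or 8 weeks; last dose at the PFS event; death closes the window at once; deaths 0%, 15% or 30% of events in the scan-dated runs.

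**The plan's own figures.** The documents state no figure for this comparison. The section supplying the 3.0-month median can be checked. The Schoenfeld formula for hazard ratio 0.70, 2:1 allocation, one-sided 0.025 and 80% power gives (1.960 + 0.842)² / [(2/9) × (ln 0.70)²] = 278 events, against 274 stated. With 274 events it gives 79.5% power at 0.70 and 91.9% at 0.65, against 80% and 92.3%. These agree closely, and the rash issue does not touch them.

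**Step 1: the mechanism.** For a patient whose PFS ends in progression on day t, with median onset m days,

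P(rash group | t) = 0.40 × [1 − 2^(−(t+28)/m)].

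Compare t = 30.4 days (1 month) with t = 182.6 days (6 months):
- m = 56 (8 weeks): 0.40 × (1 − 2^(−1.043)) = 0.21, against 0.40 × (1 − 2^(−3.761)) = 0.37.
- m = 7 (1 week): 0.40 at both, to two decimals.

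Group membership depends on PFS when onset is late and hardly at all when it is early.

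**Step 2: simulation with no true association.** 2,000 replicates per scenario; Cox model with rash as the only covariate; geometric-mean hazard ratio, rash versus no rash. The SAP plans no such model or test; the hazard ratio only measures the shift.

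| Setting | 1 wk | 2 wk | 4 wk | 8 wk |
|---|---|---|---|---|
| Progression at true date | 0.99 | 0.95 | 0.86 | 0.73 |
| Median PFS, months, rash vs none (same runs) | 3.1 vs 3.0 | 3.2 vs 2.9 | 3.5 vs 2.7 | 4.1 vs 2.6 |
| As first row, rash rate halved off drug | 0.97 | 0.90 | 0.80 | 0.68 |
| As first row, 20% rash-prone | 1.00 | 0.97 | 0.89 | 0.79 |
| As first row, 60% rash-prone | 0.99 | 0.93 | 0.80 | 0.66 |
| Scan-dated, no deaths | 1.00 | 0.99 | 0.92 | 0.80 |
| Scan-dated, 15% deaths | 0.99 | 0.96 | 0.89 | 0.77 |
| Scan-dated, 30% deaths | 0.97 | 0.93 | 0.85 | 0.74 |
| Response %, rash vs none | 10.0 vs 10.2 | 10.5 vs 10.0 | 11.1 vs 9.7 | 11.7 vs 9.6 |

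The response row allows response only in patients event-free past week 6.

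**Step 3: different assumptions.** 400,000 patients, 50% rash-prone, 20% of first events deaths, scan-dated progression, onset given by its mean. For means of 1, 2, 4, 8 and 16 weeks the hazard ratios are 0.98, 0.96, 0.91, 0.81 and 0.71; with onset uniform over 24 weeks, 0.68. Using the earlier trial's median PFS of 2.63 months, the range is 0.98 to 0.67.

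**Step 4: landmark.** Classifying by rash up to day 28, and following only patients event-free then, gives hazard ratios of 1.00-1.02 and equal response rates. The share kept is 2^(−28/91.3) = 0.81 with true-date progression. With scan-dated progression no one can progress before week 6, so only early deaths drop out: at 15% deaths about 0.15 × 0.19 = 3%. A week-6 landmark, run under the Step 3 assumptions, gives 0.99-1.01.

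**The case against.** The strongest reply is that little depends on this analysis. It is labelled exploratory, is descriptive, covers one arm, and feeds no test or decision. The SAP also plans a time-to-first-onset table for rash/acne, which tells a reader whether onset was early enough for the artefact to be negligible. That limits the priority of the point. It does not answer it, because the onset table shows how large the artefact could be without correcting the PFS comparison beside it.

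The sizes are also open to challenge. Onset, rash-prone share and death share are all assumed, and nothing in the documents supports an 8-week median onset. Treating progression as continuously observed overstates the shift, since scheduled scans begin at week 6. When dated at scans, median PFS can be identical in the two groups for 1- and 2-week onset with few deaths. All of this stands, and the scan-dated rows should be preferred. The link between treatment time and PFS is also inexact: treatment follows the investigator's assessment or adverse events, while primary PFS uses central review. Stopping early because of rash would pull the other way.

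The remedy has a weakness. Under the assumed onset model, day 28 captures 1 − 2^(−4/m) of rash-prone onsets, with m in weeks: 94%, 75%, 50% and 29% for m = 1, 2, 4 and 8. Where the bias is largest, much true rash would be classed as no rash, diluting a real association. That also stands, and is the reason to consider a time-dependent model alongside.

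Finally, SAP sections 6.4, 7.6 and 9 are not in the public text, so a rule there cannot be excluded. Section 7.8.1 refers to none for this analysis.

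**Conclusion.** The concern holds. As visible, the plan lets PFS help decide who is in the rash group, and in these simulations any appreciable shift favours rash. Its size depends on rash onset, which the documents do not give. It is slight when median onset is 1 week and usually small at 2 weeks. With scan-dated progression and 15% deaths, the hazard ratio is about 0.89 at 4 weeks and 0.77 at 8 weeks. The 28-day tail and the first scan at week 6 soften the effect without removing it. These figures assume that rash onset is unrelated to PFS and that treatment ends at the PFS event.

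The effect on response is at most about 2 percentage points in the cases tried (11.7% vs 9.6%). Confidence is high in the direction and mechanism, and limited for the magnitude. The primary and secondary analyses are not affected. This is a worthwhile, cheap improvement to an exploratory analysis.

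**What to change.** In SAP 7.8.1, make the descriptive comparison a day-28 landmark:
- Classify afatinib patients by grade 2 or higher rash/acne with onset up to day 28.
- Include only those alive and progression-free at day 28.
- Describe PFS from day 28 and response after day 28.

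Optionally add a Cox model with rash as a time-dependent covariate, which keeps the later rash that the landmark sets aside. State as a limit of interpretation that the landmark does not remove dose differences arising after day 28 from escalation.

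The cost is one paragraph and a small programming change, using onset dates already planned for tabulation. About 19% of patients leave the comparison if PFS is exponential with events at their true dates, or about 3% if progression is dated at scans and 15% of events are deaths. Rash starting after day 28 no longer counts as rash.
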